7.6.2 Analysis of Secondary Efficacy Endpoints

For continuous primary endpoints, treatment effects will be summarized descriptively according to visit.

For ordinal primary endpoints, treatment effects will be summarized descriptively according to visit.

Further details on the analysis of efficacy endpoints will be provided in the SAP. Further details on the analysis of secondary efficacy endpoints will be provided in the SAP.

7.7 Data Quality Assurance

Standard operating procedures are available for all activities relevant to the quality of this study. Designated personnel will be responsible for implementing and maintaining quality assurance and quality control systems to ensure that the study is conducted and that data are generated, documented, and reported in compliance with the study protocol, Good Clinical Practice (GCP), and Good Laboratory Practice requirements as well as applicable regulatory requirements and local laws, rules, and regulations relating to the conduct of the clinical trial.

An authorized quality assurance auditor will audit the study data and procedures at periodic intervals as indicated. Domestic or foreign regulatory authorities, the IRB, and a Sponsor-authorized auditor may request access to all study documentation for an on-site inspection or audit. The investigator must notify GTx, Inc. of any regulatory authority inspections and forward copies of the inspection report to GTx, Inc.

Electronic data systems will be in accordance with applicable aspects of 21 Code of Federal Regulations (CFR) Part 11, International Council for Harmonisation (ICH) Guidelines, GCP, local laws and legislation, and the Health Insurance Portability and Accountability Act.

7.7.1 On-Site Audits

At any time, quality assurance representatives of the Sponsor and/or regulatory bodies may visit the unit to carry out an audit of the study in compliance with regulatory guidelines and company policy. Such audits will require access to study records, documentation, and

regulatory files. At all times, subject privacy will be of utmost importance and respected. Typically, sufficient notice will be given to the investigator to prepare for the visit.

7.7.2 Data Management

As part of the responsibilities assumed by participating in the study, the investigator agrees to maintain adequate case histories for the subjects treated as part of the research under this protocol. The investigator agrees to maintain accurate eCRFs and source documentation as part of the case histories. Source documents may include, but are not restricted to, such documents as laboratory reports and 3-day voiding diaries.

Investigative site personnel will enter subject data into InForm® (the eCRF program). The analysis data sets will be a combination of these data and data from other sources (e.g., laboratory data).

Clinical data management will be performed in accordance with applicable GTx standards and data cleaning procedures to ensure the integrity of the data, e.g., removing errors and inconsistencies in the data. Adverse events and concomitant medication terms will be coded using the MedDRA, an internal validated medication dictionary.

After database lock, each study site will receive a CD-ROM containing all of their site-specific eCRF data as entered into Oracle Clinical Remote Data Capture for the study, including full discrepancy and audit history. Additionally, a CD-ROM copy of all of the study site's data from the study will be created and sent to the Sponsor for storage. PPD will maintain a duplicate CD-ROM copy for their records. In all cases, subject initials will not be collected or transmitted to the Sponsor.

8 Ethics

8.1 Institutional Review Board

Federal regulations and the ICH guidelines require that approval be obtained from an IRB before participation of human subjects in research studies. Before study onset, the protocol, informed consent, advertisements to be used for the recruitment of study subjects, and any other written information regarding this study to be provided to the subject must be approved by the IRB. Documentation of all IRB approvals and of the IRB compliance with ICH harmonised tripartite guideline E6(R2): GCP will be maintained by the site and will be available for review by the Sponsor or its designee.

All IRB approvals should be signed by the IRB chairman or designee and must identify the IRB name and address, the clinical protocol by title or protocol number or both, and the date approval or a favorable opinion was granted.

The investigator is responsible for providing written summaries of the progress and status of the study at intervals not exceeding 1 year or otherwise specified by the IRB. The investigator must promptly supply the Sponsor or its designee, the IRB, and, where applicable, the institution, with written reports on any changes significantly affecting the conduct of the study or increasing the risk to subjects.

8.2 Ethical Conduct of the Study

The study will be performed in accordance with the ethical principles that have their origin in the Declaration of Helsinki, ICH GCP, and all applicable regulations.

8.3 Subject Information and Consent

A written informed consent in compliance with US Title 21 CFR Part 50 shall be obtained from each subject before entering the study or performing any unusual or nonroutine procedure that involves risk to the subject. An informed consent template may be provided by the Sponsor to investigative sites. If any institution-specific modifications to study-related procedures are proposed or made by the site, the consent should be reviewed by the Sponsor or its designee or both before IRB submission. Once reviewed, the consent will be submitted by the investigator to his or her IRB for review and approval before the start of the study. If the ICF is revised during the course of the study, all active participating subjects must sign the revised form.

Before recruitment and enrollment, each prospective subject will be given a full explanation of the study and be allowed to read the approved ICF. Once the investigator is assured that

GTx, Inc.

Protocol: G201004 Version 1.0

GTx-024

21 May 2018

the subject understands the implications of participating in the study, the subject will be asked to give consent to participate in the study by signing the ICF.

The investigator shall retain the signed original ICF(s) and give a copy of the signed original form to the subject.

9 Investigator's Obligations

The following administrative items are meant to guide the investigator in the conduct of the study but may be subject to change based on industry and government standard operating procedures, working practice documents, or guidelines. Changes will be reported to the IRB but will not result in protocol amendments.

9.1 Confidentiality

All laboratory specimens, evaluation forms, reports, and other records will be identified in a manner designed to maintain subject confidentiality. All records will be kept in a secure storage area with limited access. Clinical information will not be released without the written permission of the subject, except as necessary for monitoring and auditing by the Sponsor, its designee, the US Food and Drug Administration (FDA), or the IRB.

The investigator and all employees and coworkers involved with this study may not disclose or use for any purpose other than performance of the study any data, record, or other unpublished, confidential information disclosed to those individuals for the purpose of the study. Prior written agreement from the Sponsor or its designee must be obtained for the disclosure of any said confidential information to other parties.

9.2 Financial Disclosure and Obligations

Investigators are required to provide financial disclosure information to allow the Sponsor to submit the complete and accurate certification or disclosure statements required under 21 CFR 54. In addition, the investigator must provide to the Sponsor a commitment to promptly update this information if any relevant changes occur during the course of the investigation and for 1 year following the completion of the study.

Neither the Sponsor nor PPD is financially responsible for further testing or treatment of any medical condition that may be detected during the screening process. In addition, in the absence of specific arrangements, neither the Sponsor nor PPD is financially responsible for further treatment of the subject's disease.

9.3 Investigator Documentation

Prior to beginning the study, the investigator will be asked to comply with ICH E6(R2) 8.2 and Title 21 of the CFR by providing the following essential documents, including but not limited to:

- IRB approval

- Original investigator-signed investigator agreement page of the protocol
- Form FDA 1572, fully executed, and all updates on a new fully executed Form FDA 1572
- Curriculum vitae for the investigator and each subinvestigator listed on Form FDA 1572
- Financial disclosure information to allow the Sponsor to submit complete and accurate certification or disclosure statements required under 21 CFR 54. In addition, the investigators must provide to the Sponsor a commitment to promptly update this information if any relevant changes occur during the course of the investigation and for 1 year after the completion of the study
- IRB-approved informed consent, samples of site advertisements for recruitment for this study, and any other written information regarding this study that is to be provided to the subject
- Laboratory certifications and normal ranges for any local laboratories used by the site, in accordance with 42 CFR 493

9.4 Study Conduct

The investigator agrees that the study will be conducted according to the principles of ICH E6(R2). The investigator will conduct all aspects of this study in accordance with all national, state, and local laws or regulations. Study information from this protocol will be posted on publicly available clinical trial registers before the enrollment of subjects begins.

9.5 Adherence to Protocol

The investigator agrees to conduct the study as outlined in this protocol in accordance with ICH E6(R2) and all applicable guidelines and regulations.

9.6 Adverse Events and Study Report Requirements

By participating in this study, the investigator agrees to submit reports of SAEs according to the timeline and method outlined in the protocol. In addition, the investigator agrees to submit annual reports to the study-site IRB as appropriate.

9.7 Investigator's Final Report

Upon completion of the study, the investigator, where applicable, should inform the institution; the investigator/institution should provide the IRB with a summary of the study's outcome and the Sponsor and regulatory authority(ies) with any reports required.

9.8 Records Retention

Essential documents should be retained until at least 2 years after the last approval of a marketing application in an ICH region and until there are no pending or contemplated marketing applications in an ICH region or at least 2 years have elapsed since the formal discontinuation of clinical development of the investigational product. It is the responsibility of the Sponsor to inform the investigator/institution as to when these events stated in 21 CFR 312.62(c) have occurred. These documents should be retained for a longer period, however, if required by the applicable regulatory requirements or by an agreement with the Sponsor.

9.9 Publications

After completion of the study, the data may be considered for reporting at a scientific meeting or for publication in a scientific journal. In these cases, the Sponsor will be responsible for these activities and will work with the investigators to determine how the manuscript is written and edited, the number and order of authors, the publication to which it will be submitted, and other related issues. The Sponsor has final approval authority over all such issues.

Data are the property of the Sponsor and cannot be published without prior authorization from the Sponsor, but data and publication thereof will not be unduly withheld.

10 Study Management

10.1 Monitoring

10.1.1 Monitoring the Study

The clinical monitor, as a representative of the Sponsor, has the obligation to follow the study closely. In doing so, the monitor will visit the investigator and study site at periodic intervals, in addition to maintaining necessary telephone and letter contact. The monitor will maintain current personal knowledge of the study through observation, review of study records and source documentation, and discussion of the conduct of the study with the investigator and personnel.

All aspects of the study will be carefully monitored, by the Sponsor or its designee, for compliance with applicable government regulation with respect to current GCP and current standard operating procedures.

10.1.2 Inspection of Records

Investigators and institutions involved in the study will permit study-related monitoring, audits, IRB review, and regulatory inspections by providing direct access to all study records. In the event of an audit, the investigator agrees to allow the Sponsor, representatives of the Sponsor, FDA, or other regulatory agency access to all study records.

The investigator should promptly notify the Sponsor and PPD of any audits scheduled by any regulatory authorities and promptly forward copies of any audit reports received to the Sponsor.

10.2 Management of Protocol Amendments and Deviations

10.2.1 Modification of the Protocol

Any changes in this research activity, except those necessary to remove an apparent, immediate hazard to the subject, must be reviewed and approved by the Sponsor or its designee. Amendments to the protocol must be submitted in writing to the investigator's IRB for approval before subjects can be enrolled into an amended protocol.

10.2.2 Protocol Deviations

The investigator or designee must document and explain in the subject's source documentation any deviation from the approved protocol. The investigator may implement a deviation from, or a change of, the protocol to eliminate an immediate hazard to study

subjects without prior IRB approval. As soon as possible after such an occurrence, the implemented deviation or change, the reasons for it, and any proposed protocol amendments should be submitted to the IRB for review and approval, to the Sponsor for agreement, and to the regulatory authorities, if required.

A deviation from the protocol is an unintended or unanticipated departure from the procedures or processes approved by the Sponsor and the IRB and agreed to by the investigator. A significant deviation occurs when there is nonadherence to the protocol by the subject or investigator that results in a significant, additional risk to the subject. Significant deviations can include nonadherence to inclusion or exclusion criteria, enrollment of the subject without prior Sponsor approval, or nonadherence to FDA regulations or ICH GCP guidelines, and will lead to the subject being withdrawn from the study (Section 4.2).

Protocol deviations will be documented by the clinical monitor throughout the course of monitoring visits. Principal investigators will be notified in writing by the monitor of deviations. The IRB should be notified of all protocol deviations in a timely manner.

10.3 Study Termination

Although GTx has every intention of completing the study, GTx reserves the right to discontinue the study at any time for clinical or administrative reasons.

The end of the study is defined as the date on which the last subject completes the last visit (includes follow-up visit).

12.1 Appendix: Schedule of Events

Table 12–1 Schedule of Events for Protocol G201004

Procedure	Baseline Day 0	V1	V2	V3	Long-term Safety	End of Study
Day or Week	Week 0	Week 4	Week 8	Week 12	Every 12 weeks following V3	30 days after last dose of GTx-024
Visit Window (days)	–	±7	±7	±7	±7	±7
Informed consent	X					
Eligibility criteria review	X					
Medical history	X					
Concomitant medications	X	X	X	X	X	X
Height ^a and weight	X	X	X	X	X	X
Vital signs	X	X	X	X	X	X
3-Day voiding diary	X	X	X	X	X	X
PGI-S	X	X	X	X	X	X
PGI-I		X	X	X	X	X
Adverse event reviews	X	X	X	X	X	X
CMP (Chem 16 panel)	X	X	X	X	X	X
CBC	X	X	X	X	X	X
Lipid panel	X	X	X	X	X	X
Hormone panel ^b	X	X	X	X	X	X
SHBG ^b	X	X	X	X	X	X
Transvaginal ultrasound ^c	X			X	X	
Dispense study drug	X	X	X	X	X	
Collect unused study drug		X	X	X	X	X

Abbreviations: CBC, complete blood count; CMP, comprehensive metabolic panel; PGI-I, Patient Global Impression of Improvement scale; PGI-S, Patient Global Impression of Severity scale; SHBG, sex hormone-binding globulin; V, visit.

^a Height is measured at baseline only.

^b During the long-term safety period, the hormone panel and SHBG will be assessed every 24 weeks only (i.e., every other clinic visit).

^c During the long-term safety period, the transvaginal ultrasound will be assessed every 24 weeks only (i.e., every other clinic visit)

12.2 Appendix: Patient Global Impression of Severity Scale

PATIENT GLOBAL IMPRESSION OF SEVERITY (PGI-S) SCALE	
Check the one number below that best describes how your urinary tract condition is now.	
 1	Normal
 2	Mild
 3	Moderate
 4	Severe

12.3 Appendix: Patient Global Impression of Improvement Scale

PATIENT GLOBAL IMPRESSION OF IMPROVEMENT (PGI-I) SCALE	
Check the one number that best describes how your urinary tract condition is now, compared with how it was before you began taking medication in this study.	
 ₁	Very much better
 ₂	Much better
 ₃	A little better
 ₄	No change
 ₅	A little worse
 ₆	Much worse
 ₇	Very much worse

1.11.2016

Staff Initials _____

Date Data Entered _____

Page 1 of 1

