the atrophy in urethral muscle that was observed in the control group. This preliminary in vivo study supports the clinical study of SARMs for the treatment of SUI.

A proof-of-concept study is currently ongoing to investigate the effect of GTx-024 on symptoms of SUI in postmenopausal women. Available data from the 18 subjects who received doses of GTx-024 3 mg once daily for 12 weeks showed a mean reduction in stress incontinence episodes of 81%, with all 18 subjects experiencing clinically significant reduction ($\geq 50\%$ reduction in stress leaks) in the number of stress incontinence episodes by Week 12.

A double-blind, placebo-controlled, parallel-design, randomized, multicenter, Phase 2 study (G201002) is currently ongoing to assess the clinical activity and safety of GTx-024 in postmenopausal women with SUI. The study consists of a screening period (4 weeks), treatment period (12 weeks), follow-up period (4 weeks), and durability period (16 weeks).

The current 12-week, open-label extension study will enroll the following subjects from G201002:

- From the first 225 subjects enrolled in G201002, only subjects randomly assigned to the placebo group and who have completed the 12-week treatment period and 16-week durability period from G201002 will be allowed to enroll in this study, once data from G201002 are unblinded. Placebo subjects who enrolled in the durability extension study (G201003) will be allowed to discontinue participation in G201003, once data from G201002 have been unblinded
- From Subject 226 onwards, any subject who was randomly assigned to any treatment group and who has completed the 12-week treatment period and the 4-week follow-up period in Study G201002 will be allowed to enroll

This open-label extension study will provide additional long-term safety and tolerability data for GTx-024. All subjects in this study will receive GTx-024 3 mg orally, once daily.

2 Study Objectives

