3.1 Study Design

This is a multicenter, Phase 2, open-label extension study that will assess the long-term safety and tolerability of GTx-024.

The current study will enroll the following subjects from G201002:

- From the first 225 subjects enrolled in G201002, only subjects randomly assigned to the placebo group and who have completed the 12-week treatment period and 16-week durability period will be allowed to enroll in this study, once data from G201002 are unblinded. Placebo subjects who enrolled in the durability extension study (G201003) will be allowed to discontinue participation in G201003, once data from G201002 have been unblinded
- From Subject 226 onwards, any subject who was randomly assigned to any treatment group and who has completed the 12-week treatment period and the 4-week follow-up period in Study G201002

All subjects in this study will receive GTx-024 3 mg orally, once daily.

The study consists of the following visits:

Baseline (Day 0)

Subjects will be evaluated, and an additional written informed consent for the open-label extension study will be obtained. Procedures will be performed at baseline as specified in the schedule of events (Table 12–1) for the study.

Long-term Open-label Extension Period

Subjects who continue to meet the eligibility criteria will attend clinic visits at 4-week intervals for the first 12 weeks of the open-label extension study (i.e., Weeks, 4, 8, and 12). Following the first 12 weeks, subjects will attend clinic visits every 12 weeks (i.e., 12 weeks from Visit 3 onwards). At each clinic visit, study procedures will be performed as specified in the schedule of events (Table 12–1).

There is currently no planned end to this study; instead, subjects will be on treatment and followed until marketing approval is granted to GTx-024 or until the withdrawal of the Investigational New Drug application. If marketing approval is granted to GTx-024, a plan

for the transition of subjects from study drug to commercial drug product or other therapy will be implemented.

Data from this open-label extension study will be used to assess the long-term safety and tolerability of GTx-024.

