6.1.1 Baseline (Day 0)

The study will be explained in detail, and adequate time will be allowed for answering questions from a potential subject before she signs the institutional review board (IRB)–approved informed consent document. Informed consent will be obtained from those potential subjects who meet initial inclusion/exclusion criteria and express willingness to participate before study site personnel conduct any study assessments of such subjects.

Once informed consent is obtained, the subjects will be assigned a subject number and a detailed interview will be conducted with the subject about her concomitant medications, and recent medical history will be evaluated. Height and weight will be measured, and vital signs will be assessed as presented in Table 12–1.

The subject’s eligibility criteria will be reviewed. During the visit, the subject will complete the PGI-S. Blood will be drawn for a comprehensive metabolic panel (CMP), complete blood count (CBC), lipid panel, hormone panel, and SHBG tests. A baseline transvaginal ultrasound examination will also be performed in subjects with an intact uterus.

The subject will be provided with a 3-day voiding diary and instructed to complete the 3-day voiding diary within the week preceding her next study visit.

Study drug will be dispensed with administration instructions. The medication identification number assigned to the subject will be noted in the eCRF for study drug accountability. The subject will take the first dose of study drug during the baseline visit. The subject will be reminded to bring all unused study drug (in its original packaging) to her next clinic visit. Any subject who prematurely discontinues the study or study drug will be asked to return to the study site and complete end-of-study assessments.

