7.2 Secondary Efficacy Endpoints

The secondary objective in this study is to assess the efficacy of GTx-024 3 mg administered once daily at each scheduled visit in relation to the following:

- Change from baseline in the mean number of stress incontinence episodes per day as measured with the 3-day voiding diary
- Change from baseline in subject-reported impression of SUI severity as measured with the PGI-S
- Improvement relative to baseline in subject-reported impression of SUI improvement as measured with the PGI-I
- Change from baseline in the mean number of urge incontinence episodes per day as measured with the 3-day voiding diary
- Change from baseline in the mean number of total incontinence episodes (stress + urge) as measured with the 3-day voiding diary

These analyses will be described in further detail in the statistical analysis plan (SAP).

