7.6 Statistical Analysis Methodology

A separate SAP will be finalized, providing detailed methods for all endpoints. In general, descriptive or summary statistics (n, mean, standard deviation, median, minimum and maximum values for continuous variables, and number [%] of subjects in each category for categorical variable) will be provided by visit. Source data for summary tables and statistical analyses will be presented as subject data listings.

All statistical analyses will be performed using SAS (version 9.3 or higher). No formal statistical analysis will be performed, as the open-label extension study is not powered for inferential statistics. Two-sided 95% confidence intervals will be provided where appropriate. No imputation will be done for missing data. The SAP will specify up to which visit summaries will be produced, as not all subjects will have been in the study for the same length of time. Further details on the analysis of efficacy endpoints will be provided in the SAP.

The study period is defined as baseline (Day 0) through end of study. Change from baseline will be between baseline (Day 0) and scheduled visits.

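### The PGI-I stem does not name the study or date it refers to, so some roll-over women may rate improvement against their state before G201002 instead of Day 0

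*Combined protocol and SAP*

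**What the plan says.** - **Form (Appendix 12.3).** The woman rates "how your urinary tract condition is now, compared with how it was before you began taking medication in this study". The form gives no study number, visit or date for that reference.
- **Endpoint (section 7.2).** One of five secondary efficacy endpoints is "Improvement relative to baseline in subject-reported impression of SUI improvement as measured with the PGI-I".
- **Baseline (section 7.6).** "Change from baseline will be between baseline (Day 0) and scheduled visits".
- **First dose (section 6.1.1).** "The subject will take the first dose of study drug during the baseline visit".
- **Who enters (section 3.1).** From the first 225 subjects of G201002, "only subjects randomly assigned to the placebo group and who have completed the 12-week treatment period and 16-week durability period". From Subject 226 onwards, "any subject who was randomly assigned to any treatment group", once the 12-week treatment and 4-week follow-up periods are complete.
- **Parent study (section 1.1).** "A double-blind, placebo-controlled, parallel-design, randomized, multicenter, Phase 2 study (G201002) is currently ongoing".
- **Administration.** Table 12-1 schedules the PGI-I at every visit after baseline but not at baseline. Sections 6.1.2 and 6.1.4 say that it is completed, section 6.1.3 does not mention it, and section 6.2.3 describes the scale. None of them says which time point the woman should have in mind.
- **Subgroups (section 7.5).** None are planned.

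**The concern.** With a recalled-change scale, the reference point exists only in the respondent's mind. The usual stem works when a participant has started study medication once. Here each woman has started blinded study treatment once in G201002 and starts treatment again in G201004. Women from Subject 226 onwards are not required to wait for unblinding, so some may not know what they received.

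A woman who was on GTx-024 in G201002 and still has some benefit at Day 0 would give a more favourable rating against her state before G201002 than against Day 0. Improvement gained in the parent study could then be counted as improvement in the extension. A woman who had become worse by Day 0 would be shifted the other way. If women differ in the reference they use, the PGI-I table mixes two quantities under one label. This is an uncontrolled study, and that descriptive table is the only PGI-I result.

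**Working it through.** The plan states no figure that can be reproduced here. The check is to set the texts side by side and measure how far apart the two possible reference points lie.

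**1. Literal reading.** G201004 has its own consent (section 3.1). Its first dose is taken at the Day 0 visit (section 6.1.1), and baseline is Day 0 (section 7.6). So the time before medication began *in this study* is Day 0 for every woman, and form and endpoint agree.

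**2. What the woman sees.** She sees the form, not those sections. The form does not say which study is meant, and no visit section has staff tell her. Agreement therefore depends on each woman choosing the literal reading unaided.

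**3. Distance between the two reference points.** These are the start of G201002 treatment and Day 0 of G201004. Inputs: treatment 12 weeks, follow-up 4 weeks, durability 16 weeks (section 1.1); 30-day consent windows (section 4.1.1). Day 0 is taken as the consent date, and visit windows are ignored.

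| Entrants | Minimum gap | Maximum gap |
|---|---|---|
| Subjects 226 to 493 | 12 + 4 = 16 weeks | 16 + 30/7 = about 20.3 weeks |
| Subjects 1 to 225 | 12 + 16 = 28 weeks, or 12 + 4 + 16 = 32 if follow-up and durability run in sequence | Depends on the unblinding date, which is not given |

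**4. How many women had GTx-024 before.** Only entrants from Subject 226 onwards can have had it. The G201002 allocation is not stated, so the placebo share *p* is an assumption. If every woman in the eligible groups enrolls, 225*p* come from Subjects 1 to 225 and 493 − 225 = 268 from the later group. The share with prior GTx-024 is 268(1 − *p*) / (225*p* + 268).

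| Assumed *p* | Prior GTx-024 / all | Share |
|---|---|---|
| 1/2 | 134 / 380.5 | 35% |
| 1/3 | 178.7 / 343 | 52% |
| 1/4 | 201 / 324.25 | 62% |

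This is the size of the group most exposed to the problem. It is not an estimate of how many would misread the form.

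**5. Can analysis recover the reference used?** No. There is no Day 0 PGI-I value to re-anchor the rating, and the form does not record which time point the woman used. Tabulating by prior arm would help interpretation but would not show which reference a given woman used. PGI-S change from Day 0 does not depend on this wording, but it cannot serve as a check on individual answers: a 4-point rating of current state and a 7-point rating of change can differ legitimately.

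**The case against.** The strongest reply is that the wording is already right. *This study* is G201004, medication in it begins on Day 0, and a woman who answers against an earlier time has misread the question. That stands as a reading of the text. It rules out the stronger inference a reader might draw, that PGI-I answers have no common reference or do not measure improvement from Day 0. The documents support only a risk that some answers are misplaced, and they give no evidence on how often.

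A reader might also infer that every entrant had already taken active drug. That is not so: entrants from Subjects 1 to 225 had placebo only and enter after unblinding, and later entrants include placebo women. For all of these, the first GTx-024 dose is in this study. What they share with the others is having been through a blinded treatment period.

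The form carries the date 1.11.2016 and the protocol is dated 21 May 2018. A reader might take this as proof that the stem was carried over without thought for roll-over women. The date is unexplained, and an older form is no defect where its words still fit.

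Finally, the primary objective is safety, the PGI-I is descriptive, PGI-S has a Day 0 value, and sections 7.2, 7.6 and 7.6.2 leave detail to a separate SAP. This limits the consequence, and the point should rank accordingly. It does not remove the need to act early, because no SAP rule can supply a reference that was never recorded.

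**Conclusion.** The point holds as a risk of mixed recall references in one of five secondary efficacy endpoints. If a woman uses the earlier reference, it lies about 16 to 20 weeks before Day 0 for Subjects 226 to 493 and at least 28 weeks before it for Subjects 1 to 225, given the stated period lengths and Day 0 at consent. The concern that drug benefit from the parent study is credited to the extension applies only to women previously on GTx-024.

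The effect on the PGI-I distribution cannot be sized from the documents. They give neither the rate of misreading nor women's state at Day 0 relative to before G201002. The proof-of-concept result in section 1.1 does not help: it is a reduction in diary episodes among 18 women in another study, and nothing maps it to PGI-I categories. This is a minor but worthwhile clarification, best made before PGI-I data are collected. It leaves the safety objective untouched.

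**What to change.** 1. On the form in Appendix 12.3, add a line with the Day 0 date pre-filled by the site, for example: *In this question, this study means the open-label extension (G201004). Please compare with your condition just before your first dose in it, on [Day 0 date].* Leave the seven response items and the rest of the stem unchanged.
2. Put the same standard instruction in sections 6.1.2, 6.1.3, 6.1.4 and 6.2.3, for staff to give before the PGI-I is completed. Section 6.1.3 should also list the PGI-I, since Table 12-1 schedules it at the long-term visits.

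The cost is one form revision and one site instruction. The downside is a small addition to a stem that section 6.2.3 relies on as validated. Adding a date and a clarification, and not rewriting the question, keeps that departure slight. The change cannot help answers already given, so it should be in place before the first Week 4 visit.
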